8.2 Secondary Efficacy Analyses

Endpoint	
 Disease state on a 7-point scale at Day 7, 14 and 28 (or last observation if discharged or died prior to this time point) defined as: 
 death, hospitalized, on invasive mechanical ventilation or ECMO, hospitalized, on non-invasive ventilation or high flow oxygen devices, Hospitalized, requiring low flow supplemental oxygen, hospitalized, not requiring supplemental oxygen - requiring ongoing medical care (COVID-19 related or otherwise), hospitalized, not requiring supplemental oxygen - no longer requires ongoing medical care, not hospitalized
----------	-------------------------------------------------------------------------------------------------------------------------------------------------------------------------------------------------------------------------------------------------------------------------------------------------------------------------------------------------------------------------------------------------------------------------------------------------------------------------------------------------------------------------------------------------------------------------------------------------------------------------------------------------------------------------------------------------------------------------------------

Analysis population	
 Full population analysis
Descriptive statistics and graphical representation	
 Data will be summarized with proportion and 95% confidence interval globally and according to disease severity at baseline (ORDSC score 2 vs 3-4 vs 5) Proportional odds models will be used to compared the 3 groups P-values will be two-tailed with a significant level at 5%.
Statistical analysis	
The proportions will be calculated by the number of subjects in each category divided by the total number of subjects in the full analysis population.
 
Subjects with missing clinical status will be considered deceased
 
The associated two-sided 95% exact confidence intervals will be calculated using Clopper–Pearson method

Endpoint	2. Disease severity at day 7, 14, and 28 as assessed by NEWS 2 score
Analysis population	
 Full population analysis
Descriptive statistics and graphical representation	
 Data will be summarized with mean and 95% confidence interval globally and according to disease severity at baseline (ORDSC score 2 vs 3-4 vs 5) Linear mixed models will be used to compared the 3 groups P-values will be two-tailed with a significant level at 5%. The evolution curves will be plotted
Statistical analysis	
The changes from baseline in NEWS 2 score within group will be compared using mixed models for repeated measures with random intercept and unstructured covariance matrix, adjusted for baseline value. Subjects who die will be imputed as a score of 20 and subjects who are discharged will be imputed a score of 2. The sample size is quite large to consider the residuals of the mixed model is normally distributed. Time will be considered as categorical variable

Endpoints	3.1. Occurrence of SpO2 >94% on room air on day 7, 14 and 28 3.2. Time to SpO2 > 94% on room air
Analysis population	
 Full population analysis
Descriptive statistics and graphical representation	
 Data will be summarized with proportion and 95% confidence interval for the occurrence of SpO2 >94% on room air and median and 95% confidence interval for time to SpO2>94%. Data will be summarized globally and according to disease severity at baseline (ORDSC score 2 vs 3-4 vs 5)

	
 • LogRank test will be used to compared the 3 groups • P-values will be two-tailed with a significant level at 5% • Kaplan-Meier curves will be plotted
Statistical analysis	
Kaplan-Meier estimates will be used to calculate the proportion and the median time as well as the associated 95% confidence intervals
 
Time to event will be defined as the time between the date of first symptom and the date of the event of interest or hospital discharge or last observation
 
Subjects who died with $\text{SpO}_2 \leq 94\%$ will be censored at day 28

Endpoints	4.1. Frequency of oxygen therapy overall and by type (low versus high flow oxygen) 4.2. Duration (days) of oxygen therapy 5. Frequency of ICU admission 6. Number of days spent in ICU/ITU 7.1. Frequency of mechanical ventilation/ECMO of hospitalization 7.2. Time on mechanical ventilation/ECMO
Analysis population	
 • Full population analysis
Descriptive statistics and graphical representation	
 • Data will be summarized with proportion or median and 95% confidence interval according to the endpoint • Data will be summarized globally and according to disease severity at baseline (ORDSC score 2 vs 3-4 vs 5) • LogRank test will be used to compared the 3 groups • P-values will be two-tailed with a significant level at 5% • Kaplan-Meier curves will be plotted
Statistical analysis	
Kaplan-Meier estimate will be used to estimate the proportion of subject with oxygen therapy and by type (low versus high flow oxygen), the proportion of subjects admitted in ICU and the proportion of those having received mechanical ventilation or ECMO. Time to event will be defined as the time between the date of first symptom and the date of event of interest. Participants not experienced the event of interest will be censored at last observation date. Participants who deceased before will be considered as having the event.
 
The duration (days) of oxygen therapy, the number of days spent in ICU/ITU and the time (days) on mechanical ventilation/ECMO will be estimated using Kaplan-Meier estimates as well as the associated 95% confidence intervals. The time will be defined as the time between the start date of event and the end date of the event of interest or hospital discharge. Subjects who died will be censored at day 28.

Endpoint	8. Duration (days) of hospitalization
----------	----------------------------------------------

Analysis population	
 Full population analysis
Descriptive statistics and graphical representation	
 Data will be summarized with median and 95% confidence interval globally and according to disease severity at baseline (ORDSC score 2 vs 3-4 vs 5) LogRank test will be used to compared the 3 groups P-values will be two-tailed with a significant level at 5% Kaplan-Meier curves will be plotted
Statistical analysis	
Kaplan-Meier method will be used to calculate the medians and the 95% confidence intervals. Time (days) from hospitalization to hospital discharge will be defined as the time between the date of hospitalization for COVID-19 and the date of hospital discharge. The event will be hospital discharge. Subjects who died will be censored at day 28.

9. Other Analyses

Endpoints	9.1. Time (days) from first symptom to use of Remdesivir 9.2. Time (days) from hospitalization to use of Remdesivir 9.3. Duration (days) of use of Remdesivir
Analysis population	
 Full population analysis
Descriptive statistics and graphical representation	
 Data will be summarized with median and 95% confidence interval globally and according to disease severity at baseline (ORDSC score 2 vs 3-4 vs 5) LogRank test will be used to compared the 3 groups P-values will be two-tailed with a significant level at 5% Kaplan-Meier curves will be plotted.
Statistical analysis	
Kaplan-Meier method will be used to calculate the medians and the 95% confidence intervals of the time to use of Remdesivir. Time (days) from first symptom to use of Remdesivir will be defined by the time between the date of first symptom and the start date of Remdesivir. The event will be the exposure to Remdesivir therapy at least one time during the hospitalization period
 
The time (days) from hospitalization to the use of Remdesivir will be estimate using the Kaplan-Meier method as well as the 95% confidence interval. The event will be the first use of Remdesivir.
 
Duration (days) of use of Remdesivir will be estimated using the Kaplan-Meier method. The time is defined as the time between the start date of Remdesivir and the end date of Remdesivir. The event will be the discontinuation of the use of Remdesivir.

Endpoints	10.1. Frequency of re-admission with COVID within 28 days of discharge 10.2. Frequency of discharge after re-admission 10.3. Frequency of death after re-admission
Analysis population	
 For 10.1, the analysis population will be all subjects who discharge from hospital within the first 28 days For 10.2 and 10.3, the analysis population will be all re-admitted subjects
Descriptive statistics and graphical representation	Data will be summarized with number of subjects with an event out of the total number of analyzed population Data will be summarized globally and according to disease severity at baseline (ORDSC score 2 vs 3-4 vs 5) Chi square test will be used to compared the 3 groups P-values will be two-tailed with a significant level at 5%
Statistical analysis	The frequency will be estimated by the number of events divided by the total number of analyzed population. . The associated two-sided 95% exact confidence intervals will be calculated using Clopper–Pearson method

11. Reporting Conventions

P-values ≥ 0.001 will be reported to 3 decimal places; p-values less than 0.001 will be reported as “ <0.001 ”. The mean, standard deviation, and any other statistics other than quantiles, will be reported to one decimal place greater than the original data. Quantiles, such as median, or minimum and maximum will use the same number of decimal places as the original data. Estimated parameters, not on the same scale as raw observations (e.g. regression coefficients) will be reported to 3 significant figures.

12. Technical Details

Data will be analysed using the IBM SPSS® statistics software version 24, Stata® SE software version 13 and SAS® software version 9.4.

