2.2 Secondary objectives

The secondary objectives are to assess the clinical course and outcome of adults with COVID-19 who have been treated with Remdesivir with respect to the following:

1. a 7-point ordinal clinical status scale on Day 7 and Day 14
2. timing (from first symptoms and from hospitalisation) and duration of use of Remdesivir
3. clinical severity at Day 7, 14, 28 as assessed by the NEWS 2 score
4. clinical status as assessed a 7-point ordinal scale on Day 28 (or at last observation if discharged or died prior to this time point) in those still hospitalised after Day 14.
5. SpO₂ > 94% on room air on day 7, 14 and 28
6. duration and type (low versus high flow) of oxygen therapy (days)
7. admitted to ICU (yes versus no)
8. number of days spent on ICU/ITU
9. use of mechanical ventilation/ECMO (extracorporeal membrane oxygenation); start and stop dates
10. re-admission with COVID-19 complications or recurrence within 28 days of discharge and outcome (discharged or deceased)

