2.3 Primary Criteria for Evaluation

1. All-cause mortality at day 28
2. Clinical status assessed by a 7-point ordinal scale on Day 14 or at last observation if discharged or died prior to this time point, where the 7-point ordinal scale is defined as:
 1. Death
 2. Hospitalised, on invasive mechanical ventilation or ECMO
 3. Hospitalised, on non-invasive ventilation or high flow oxygen devices
 4. Hospitalised, requiring low flow supplemental oxygen
 5. Hospitalised, not requiring supplemental oxygen - requiring ongoing medical care (COVID-19 related or otherwise)
 6. Hospitalised, not requiring supplemental oxygen - no longer requires ongoing medical care
 7. Not hospitalised

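### The ordinal status rule freezes a discharged patient at the last observation, so anyone back in hospital on Day 7, 14 or 28 keeps the discharge status

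*SAP*

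**What the plan says.** SAP 8.2, endpoint 1, defines disease state on the 7-point scale at Days 7, 14 and 28 "or last observation if discharged or died prior to this time point". Protocol 2.3 makes Day-14 status a primary criterion with the same substitution: "or at last observation if discharged or died prior to this time point". The data schedules (protocol section 5 and Appendix 1; SAP 4.2) replace the scheduled record in the same way once a patient has been discharged.

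For this endpoint the SAP uses as denominator the "number of subjects in each category divided by the total number of subjects in the full analysis population". Its only other handling rule is "Subjects with missing clinical status will be considered deceased".

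Protocol 2.2, item 10, sets a separate objective: "re-admission with COVID-19 complications or recurrence within 28 days of discharge and outcome (discharged or deceased"). SAP section 9 analyses this as endpoints 10.1 to 10.3, the last being "10.3. Frequency of death after re-admission". For 10.1, "the analysis population will be all subjects who discharge from hospital within the first 28 days". Neither document links endpoint 10 to endpoint 1.

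**The concern.** Status on a given day should describe the patient on that day. Under this rule, discharge closes the record for the ordinal scale. A patient who goes home, deteriorates and is back in hospital at the assessment is reported at the earlier and usually better status, while the study separately sets out to record that the patient came back.

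Day-14 status is a primary criterion in protocol 2.3 and the outcome of the proportional odds model in protocol 6.3. On Day 28 the SAP widens the reach of the rule. Protocol 2.2 and 2.4 restrict Day-28 status to patients still hospitalised after Day 14, whereas SAP 8.2 applies it to the full analysis population. The status of patients discharged early is thus carried forward as far as Day 28.

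**Working it through.** **What the rule gives, case by case.** Take a patient discharged on Day 5 and re-admitted on Day 10.

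- *Alive and on invasive ventilation on Day 14.* The patient was discharged before Day 14, so the rule takes the last observation tied to that discharge. True status is category 2. No text moves the patient there.
- *Dead on Day 13.* The rule names both discharge and death before the time point, and both apply. One reading scores the Day-5 observation and the other scores category 1. No order of precedence is given.
- *At home and well on Day 14.* The last observation may mean category 7 or the last category seen in hospital (for example 5 or 6). The schedules use the same phrase for SpO2, laboratory tests and oxygenation, which suggests a pre-discharge observation. The choice matters: for a patient at category 5 on Day 1, scoring 7 is a gain of 2 points and meets the improvement criterion in protocol 2.4, item 1. Scoring 5 or 6 is a gain of 0 or 1 and does not.

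NEWS 2 shows that the SAP can be explicit: endpoint 2 assigns 20 to patients who die and 2 to those discharged. Endpoint 1 has no equivalent for discharge.

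**Size.** There is no figure in the plan to reproduce. The documents state no re-admission rate, no post-discharge death rate and no expected ordinal distribution. The following is an illustration for Day 28, taking discharge as category 7.

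Inputs: N = 450 (SAP section 5, the planned minimum). Assumed: share discharged by Day 28, *d* = 70 to 90%; share of those re-admitted, *r* = 2 to 10%; share of the re-admitted who are in hospital or dead on Day 28, *s* = 25 to 100%.

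Patients wrongly left in category 7 = N × *d* × *r* × *s*. Overstatement in percentage points = that number / N × 100. Intervals are Clopper–Pearson 95%, the SAP's method for this endpoint.

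| Case | Calculation | Patients | Category 7 by the rule | Category 7 by actual status | Difference |
|---|---|---|---|---|---|
| Low | 450 × 0.70 × 0.02 × 0.25 = 1.6 | 2 | 70.0% (65.5–74.2) | 69.6% (65.1–73.8) | 0.4 |
| Mid | 450 × 0.80 × 0.05 × 0.50 = 9 | 9 | 80.0% (76.0–83.6) | 78.0% (73.9–81.7) | 2.0 |
| High | 450 × 0.90 × 0.10 × 1.00 = 40.5 | 40 | 90.0% (86.8–92.6) | 81.1% (77.2–84.6) | 8.9 |

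The interval half-width is roughly 3 to 4.5 points. The mid-range shift lies inside it; only the upper end goes clearly beyond it. If deaths after discharge are read as category 1, they leave the count and the figures fall. No Day-7 or Day-14 figure is computed, because that would need assumptions about when discharge and re-admission occur.

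**The case against.** The strongest reply is that this is a request for clarification and not an error. The rule mentions death, so a later death can be read as the last observation. SAP section 2 states no formal hypothesis, and Part 1 has no comparator, so no treatment effect is biased. The SAP makes 28-day mortality its only primary endpoint, and protocol 2.2 lists Day-14 status as a secondary objective despite its place in 2.3. Re-admissions are reported openly in the same Table 2.

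Much of this stands, and it rules out several stronger readings that a reader might reach:

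- *Patients who die after discharge are scored as discharged.* This is one reading only. The text gives no precedence, so for deaths the fault is ambiguity.
- *The rule can only flatter the results.* That holds only if discharge means 7. If an in-hospital category is carried forward, patients at home look worse than they are. The rule that missing status counts as deceased also pushes towards a worse outcome.
- *Table 2 must contradict itself on deaths.* Endpoint 10.3 counts deaths among re-admitted patients, with re-admission timed from discharge and no Day-28 limit from admission. Category 1 also takes in missing status, whereas the mortality analysis censors it. These rows need not agree even under a correct rule.
- *Every re-admission is a misclassification.* Re-admissions can start after Day 28 or be over by then. In the mid-range case above, all re-admissions would be 18 (450 × 0.80 × 0.05), of which half are affected.

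The reply does not answer the case of a patient alive and back in hospital on the assessment day. There the rule as written gives a wrong category, and showing re-admissions elsewhere in Table 2 does not correct it.

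**Conclusion.** The concern holds for patients alive and re-admitted on Day 7, 14 or 28: the stated rule keeps their discharge status, and the re-admission information required for endpoint 10 is not used. Two gaps go with it: no precedence between discharge and later death, and no definition of the category that discharge represents. The SAP's wider Day-28 population extends the effect to patients discharged before Day 14.

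If discharge is scored 7, the error is towards a better outcome, by about 0.4 to 8.9 percentage points of category 7 on Day 28 at N=450 and about 2 points (9 patients) in the mid-range case. These sizes rest wholly on assumed discharge and re-admission rates. At low rates the effect is small beside the sampling error. The SAP's primary mortality analysis is defined separately and does not use this rule. The change is worth making because it is cheap and two analysts could otherwise score the same discharged patient differently.

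**What to change.** Replace the last-observation wording in SAP 8.2, endpoint 1, and align protocol 2.3. For each of Days 7, 14 and 28:

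1. Score 1 if the patient is dead by that day on any available record, including a re-admission record.
2. Score the in-hospital category (2 to 6) if the patient has been re-admitted and is in hospital on that day.
3. Score 7 if the patient was discharged alive and is not known to be back in hospital. Say that the missing-equals-deceased rule does not apply to these patients.

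Where the category during re-admission is not recorded, report the patient as re-admitted and not as 7, and give a sensitivity range, for example with all such patients at 2 and then at 6. State which Day-28 population applies, since the protocol and SAP differ.

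Cost: new SAP text and a link between the ordinal and re-admission data. The schedules list neither re-admission dates nor ordinal status during re-admission, and deaths after discharge without re-admission are not listed as collected. The sponsor should therefore confirm what the eCRF holds. Some further extraction at the sites may be needed, limited to the few re-admitted patients.

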2.4 Secondary Criteria for Evaluation

1. Proportion of clinical improvement at Day 14, defined as a \geq 2-point improvement from Day 1 on a 7-point ordinal scale
2. Timing and duration (days) of Remdesivir
3. Severity of disease on Day 7, Day 14 and Day 28 based on NEWS 2 score
4. Clinical status assessed by a 7-point ordinal scale on Day 28 (or at last observation if discharged or died prior to this time point) in those still hospitalised after day 14.
5. Time to SpO₂ $>$ 94% on room air (number of days when evaluation made on day 7, 14 or 28)
6. Duration of oxygen therapy (total days)
7. Admitted to ICU
8. Need for and time on mechanical ventilation/ECMO of hospitalisation
9. Duration of hospitalisation

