5 TRIAL PROCEDURES

Only real-world retrospective data will be used for this study. Deidentified retrospective data will be extracted at each clinical site from source data. No personal identifiable data will be transmitted to NEAT ID. Data will be extracted/transcribed in to the eCRF database with standard formatting from electronic medical record (EMR) databases, clinical registries, case series or additional sources from sites/ countries. The data elements will be extracted/transcribed from source data according to the following schedule. Mechanisms to ensure data quality and integrity will be deployed as per applicable standard operating procedures.

	Day1 (Hospital Admission)	Day7 (+/- 1 day) and Day14 (+/- 2 days) / last observation if discharged or died prior to these time points.	Day 28 or last observation after Day 14 if discharged or died prior to this time point.
Medical History ^a	X		
Pregnancy test	X		
HIV test	X		
Vital Signs ^b	X	X	X
Laboratory Testing ^c	X	X	X
Oxygenation ^d	X	X	X
Clinical Status ^e	X	X	X
Other Treatments for COVID-19 ^f	X	X	X
NEWS SCORE ^g	X	X	X

- a. Focused medical history and also the following information (e.g. demographics including ethnicity, baseline characteristics including DM, CV disease and COPD)
- b. SpO₂, body temperature, body weight and height on admission
- c. Includes white blood cell count, creatinine, total bilirubin, ALT, AST at admission Day 7 and day 14 or at discharge if before day 14, radiographic findings at baseline and as available and SARS-CoV-2 pcr, antigen and/or antibody testing.
- d. Includes oxygen supplementation: room air, low flow O₂ (L/min and %), high flow O₂ (L/min and %), non- invasive

positive pressure ventilation (FiO2 or %), mechanical ventilation (FiO2 or %), ECMO (extracorporeal membrane oxygenation)

- e. The ordinal scale is as: 1. Death, 2. Hospitalised, on invasive mechanical ventilation or ECMO, 3. Hospitalised, on non-invasive ventilation or high flow oxygen devices, 4. Hospitalised, requiring low flow supplemental oxygen, 5. Hospitalised, not requiring supplemental oxygen - requiring ongoing medical care (COVID-19 related or otherwise), 6. Hospitalised, not requiring supplemental oxygen - no longer requires ongoing medical care, 7. Not hospitalised

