Secondary 
 a 7-point ordinal clinical status scale on Day 7, 14 and 28 (or at last observation if discharged or died prior to this time point) clinical severity at Day 7, 14, 28 as assessed by the NEWS 2 score $\text{SpO}_2 > 94\%$ on room air on day 7, 14 and 28 duration and type (low versus high flow) of oxygen therapy (days) admitted to ICU (yes versus no) number of days spent on ICU/ITU use of mechanical ventilation/ECMO (extracorporeal membrane oxygenation); start and stop dates duration of hospitalisation timing (from first symptoms and from hospitalisation) and duration of use of Remdesivir re-admission with COVID-19 complications or recurrence within 28 days of discharge and outcome (discharged or deceased) 	
 Disease state on a 7-point scale defined as 1. death, 2. hospitalised, on invasive mechanical ventilation or ECMO, 3. hospitalised, on non-invasive ventilation or high flow oxygen devices, 4. Hospitalised, requiring low flow supplemental oxygen, 5. hospitalised, not requiring supplemental oxygen - requiring ongoing medical care (COVID-19 related or otherwise), 6. hospitalised, not requiring supplemental oxygen - no longer requires ongoing medical care, 7. not hospitalised at Day 7 and 14, and 28 (or at last observation if discharged or died prior to this time point) Occurrence of disease severity at day 7, 14, 28 as assessed by NEWS2 score SpO_2 on room air on day 7, 14, and 28 
 Occurrence of $\text{SpO}_2 > 94\%$ on room air on day 7, 14 and 28 Time to $\text{SpO}_2 > 94\%$ on room air Oxygen therapy over the 28 days 
 Frequency of oxygen therapy overall and by type (low versus high flow oxygen) Duration (days) of oxygen therapy Frequency of ICU admission Number of days spent in ICU/ITU Mechanical ventilation over the 28 days

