4.2 Study Variables

All the study variables are summarized in the following table.

	Day1 (Hospital Admission) baseline	Day 7 (+/- 1 day) and Day14 (+/- 2 days) / last observation if discharged or died prior to these time points.	Day 28 or last observation after Day 14 if discharged or died prior to this time point.
Medical History ^a	x		
Pregnancy test	x		
HIV test	x		
Vital Signs ^b	x	x	x
Laboratory Testing ^c	x	x	x
Oxygenation ^d	x	x	x
Clinical Status ^e	x	x	x
Other Treatments for COVID-19 ^f	x	x	x
NEWS SCORE ^g	x	x	x

a. Focused medical history and also the following information (e.g. demographics including ethnicity, baseline characteristics including DM, CV disease and COPD)

b. SpO2, body temperature, body weight and height on admission

c. Includes white blood cell count, creatinine, total bilirubin, ALT, AST at admission Day 7 and day 14 or at discharge if before day 14, radiographic findings at baseline and as available and SARS-CoV-2 PCR, antigen and/or antibody testing.

d. Includes oxygen supplementation: room air, low flow O2 (L/min and %), high flow O2 (L/min and %), non-invasive positive pressure ventilation (FiO2 or %), mechanical ventilation (FiO2 or %), ECMO (extracorporeal membrane oxygenation)

e. The ordinal scale is as: 1. Death, 2. Hospitalised, on invasive mechanical ventilation or ECMO, 3. Hospitalised, on non-invasive ventilation or high flow oxygen devices, 4. Hospitalised, requiring low flow supplemental oxygen, 5. Hospitalised, not requiring supplemental oxygen - requiring ongoing medical care (COVID-19 related or otherwise), 6. Hospitalised, not requiring supplemental oxygen - no longer requires ongoing medical care, 7. Not hospitalised

f. These include corticosteroids, anticoagulants, azithromycin/other antibiotics, anti-inflammatory agents (e.g. Tocilizumab), investigational agents (eg hydroxychloroquine) and immunotherapies such as convalescent plasma and monoclonal antibodies.

g. NEWS 2 score is based on Respiration rate (per minute), SpO2 (%) Air or oxygen. Systolic blood pressure (mmHg), Pulse (per minute) Consciousness, Temperature (°C)

For the purpose of the analyses, partial dates will be extrapolated. For example, all dates saved as NK/FEB/2020 will be recoded as 15/FEB/2020 and those saved NK/NK/2020 will be recoded as 15/JUNE/2020. NK means not known.

5. Sample Size calculation

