	Alert				
	Verbal				
	Pain				
	Unresponsive				

NEWS 2 score, median (IQR)						
	Low (score 0-4), n(%)					
	Medium (score 5-6)					
	High (score 7 or more)					
COVID Vaccination, n(%)						
Other treatment for COVID-19, n (%)						
	Corticosteroids					
	Tocilizimab/Sarilumab					
	Other COVID Treatment Related Drug					

Table 2. Primary and secondary outcomes

	Overall Total N=xxx	Ordinal Scale Category			
		Score of 2 N=xxx	Score of 3-4 N=xxx	Score of 5 N=xxx	P- value
Mortality over entire study period					
Number of deaths by Day 28					
Kaplan-Meier estimate of mortality by Day 28 – % (95% CI)					
Ordinal Scale at day 7 (± 1 day) – no. (%)					
1					
2					
3					
4					
5					
6					
7					
Ordinal Scale at day 14 (± 2 days) – no. (%)					
1					
2					
3					
4					
5					
6					
7					
Ordinal Scale at day 28 (± 2 days) – no. (%)					
1					
2					
3					
4					
5					
6					
7					
Disease severity assessed by NEWS 2 Score at 7 days					
Total N					
Mean NEWS 2 Score at days 7 (95% CI)					
Disease severity assessed by NEWS 2 Score at 14 days					
Total N					
Mean NEWS 2 Score at days 14 (95% CI)					
Disease severity assessed by NEWS 2 Score at 28 days					

Total N					
Mean NEWS 2 Score at days 28 (95% CI)					
SpO2>94% over first 7 days					
Number of SpO2>94% by Day 7					
Kaplan-Meier estimate of by Day 15 – % (95% CI)					
SpO2>94% over first 14 days					
Number of SpO2>94% by Day 14					
Kaplan-Meier estimate of SpO2>94 by Day 14 – % (95% CI)					
SpO2>94% over entire study period					
Number of SpO2>94% by Day 28					
Kaplan-Meier estimate of SpO2>94 by Day 28 – % (95% CI)					
Median time to SpO2>94% (95% CI) - days					
Oxygen therapy over entire study period (low or high flow)					
Number of oxygen therapy by Day 28					
Kaplan-Meier estimate of oxygen therapy by Day 28 – % (95% CI)					
Median duration on oxygen therapy (95% CI) - days					
Low flow oxygen therapy over entire study period					
Number of low flow oxygen therapy by Day 28					
Kaplan-Meier estimate of low flow oxygen therapy by Day 28 – % (95% CI)					
High flow oxygen therapy over entire study period					
Number of high flow oxygen therapy by Day 28					
Kaplan-Meier estimate of high flow oxygen therapy by Day 28 – % (95% CI)					
ICU admission over entire study period					
Number of ICU admission by Day 28					
Kaplan-Meier estimate of ICU admission by Day 28 – % (95% CI)					
Median duration spent in ICU (95% CI) - days					

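### The protocol limits Day-28 ordinal status to patients still in hospital after Day 14; the SAP reports it on the full analysis population without saying so, so the protocol's endpoint has no row of its own

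*SAP*

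**What the plan says.** **Protocol.** Section 2.2 item 4 lists Day-28 ordinal status as a secondary objective "in those still hospitalised after Day 14". Section 2.4 item 4 repeats this as a criterion for evaluation, "in those still hospitalised after day 14", and both synopsis lists carry the same limit. The Day-7 and Day-14 ordinal items (2.2 item 1, 2.3 item 2) have no such limit.

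**SAP.** Section 3 treats the three time points alike: disease state is taken "at Day 7 and 14, and 28 (or at last observation if discharged or died prior to this time point", with no mention of remaining in hospital. Section 6.2 places all secondary endpoints on the Full Analysis Population. Section 8.2 endpoint 1 gives the denominator: the number in each category is "divided by the total number of subjects in the full analysis population". It also counts a missing clinical status as death. Table 2 has one Day-28 block, overall and by baseline severity, with no block for prolonged stayers.

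**Schedule and window.** The Day-28 column, worded the same way in Protocol 5, Protocol Appendix 1 and SAP 4.2, is headed "Day 28 or last observation after Day 14 if discharged or died prior to this time point" and has no plus-or-minus window. The neighbouring column does: "Day7 (+/- 1 day) and Day14 (+/- 2 days) / last observation if discharged or died prior to these time points". Table 2 of the SAP nevertheless labels its row "Ordinal Scale at day 28 (± 2 days").

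**The concern.** One endpoint name covers two quantities. The protocol asks what happens by Day 28 to patients with a long stay. The SAP describes where the whole cohort stands on Day 28, a distribution that includes everyone discharged or dead in the first two weeks. If most patients leave hospital early, the SAP figure mainly reflects them.

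The SAP neither acknowledges nor justifies the change. A reader who takes the definition from the protocol and the number from Table 2 would attribute whole-cohort percentages to prolonged stayers, which would make their discharge rate look too high and their mortality too low. The stayers' own N, exact interval and comparison across the three severity groups would not appear.

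**Working it through.** The plan states no figure for this endpoint (SAP section 5 says no formal sample-size calculation is made), so there is nothing to reproduce. The check compares the two definitions and then illustrates the difference.

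**Definitions.** Split the N patients into S still in hospital after Day 14, E dead by then and D discharged by then, so N = S + E + D. Among the S stayers, let d be dead and h be discharged by Day 28.

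- Protocol: death = d/S; not hospitalised = h/S.
- SAP: death = (E + d)/N; not hospitalised = (D + h)/N.

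The SAP figure is a weighted average of stayers and early leavers. The gap for not hospitalised is therefore (1 − S/N) × [D/(N − S) − h/S]. It vanishes only if nobody left or died early, or if early leavers and stayers have the same discharged share.

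**Inputs.** N = 450 is the planned minimum in both documents. Everything else is assumed: S = 10–40% of N, E = 5% or 10% of N, and stayers' Day-28 status 50% discharged, 25% dead and 25% still in hospital. Counts are rounded to whole patients.

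| S | E | D | Not hospitalised, protocol | Not hospitalised, SAP | Gap (points) | Death, protocol | Death, SAP | Gap (points) |
|---|---|---|---|---|---|---|---|---|
| 45 | 22 | 383 | 22/45 = 48.9% | 405/450 = 90.0% | 41.1 | 11/45 = 24.4% | 33/450 = 7.3% | 17.1 |
| 90 | 22 | 338 | 45/90 = 50.0% | 383/450 = 85.1% | 35.1 | 22/90 = 24.4% | 44/450 = 9.8% | 14.7 |
| 180 | 22 | 248 | 90/180 = 50.0% | 338/450 = 75.1% | 25.1 | 45/180 = 25.0% | 67/450 = 14.9% | 10.1 |
| 45 | 45 | 360 | 22/45 = 48.9% | 382/450 = 84.9% | 36.0 | 11/45 = 24.4% | 56/450 = 12.4% | 12.0 |
| 180 | 45 | 225 | 90/180 = 50.0% | 315/450 = 70.0% | 20.0 | 45/180 = 25.0% | 90/450 = 20.0% | 5.0 |

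Check of the gap formula on the second row: (1 − 90/450) × (338/360 − 45/90) = 0.8 × 0.439 = 35.1 points.

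**Precision.** For the second row, the SAP's Clopper–Pearson method gives 95% intervals as follows.

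- Not hospitalised: 39.3–60.7% (protocol) against 81.5–88.3% (SAP).
- Death: 16.0–34.6% (protocol) against 7.2–12.9% (SAP).

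The protocol version is also much less precise, because it rests on 45 to 180 patients rather than 450.

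**The case against.** **The SAP may set the population.** Protocol 6.3 defines a general analysis population of enrolled patients with baseline data and leaves analysis details to the SAP. That governs who is analysed overall and by what method; it does not lift a limit written into one endpoint. Nor is the SAP bound to a single denominator: endpoints 10.1 to 10.3 have their own restricted populations.

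**The stayers' result can be recovered.** This largely stands. Table 2 gives the ordinal distribution at Days 14 and 28 on the same denominator. In the second row of the illustration, subtraction gives deaths of 44 − 22 = 22 and discharges of 383 − 338 = 45 among 90 stayers, which is the protocol result. It would be wrong to say the SAP hides these outcomes. The recovery is only approximate once statuses are missing or patients are readmitted, and it supplies no labelled row, interval or group comparison.

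**The schedule is not a clear restriction.** A reader might infer from the Day-28 column that a patient discharged on Day 9 has no Day-28 entry, and that the missing-status rule then makes that patient a death. Taken literally, this would put Day-28 deaths at 315/450 = 70.0% to 416/450 = 92.4% across the scenarios above. The documents do not support that as the intended analysis. The schedule restricts only by implication, its preceding column already captures the last observation of early leavers, and the SAP's last-observation wording is naturally read as placing them in category 7 or 1. What remains is that the SAP does not say which rule takes precedence.

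**The window is minor.** A reader might also infer that the two-day window lets deaths on Day 29 or 30 into category 1. No text says so; it is a label in a table shell, and it does not drive the difference between the two versions.

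**Conclusion.** The conflict over population holds. The protocol's Day-28 ordinal endpoint concerns prolonged stayers, the SAP's concerns the whole cohort, and the SAP does not record the change.

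The direction of the difference follows whenever early leavers are mostly discharged alive and stayers fare worse. Its size cannot be taken from the documents. The range of roughly 20–41 points for not hospitalised and 5–17 points for death rests on the assumed rates and on a single assumed outcome split among stayers.

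This is one descriptive secondary endpoint in a study with no formal hypothesis, so the consequence is a misread or unreported result rather than a wrong primary conclusion. The documents do not support a claim that early discharges will be counted as deaths, or that the Day-28 window alters the result materially. Both are points of wording to settle alongside the main change.

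**What to change.** 1. In SAP 8.2 endpoint 1 and Table 2, keep the full-population Day-28 row and add a separately labelled block for patients still in hospital after Day 14. Give it its own N, Clopper–Pearson intervals and comparison across the three baseline severity groups. State in SAP section 3 that this block is the protocol endpoint and that the full-population row is additional.
2. State that patients discharged or dead before Day 14 carry their last known status (category 7 or 1) into the full-population row and do not fall under the rule that counts missing status as death. A patient known to be readmitted and in hospital on Day 28 should be classed as hospitalised.
3. Reconcile the Day-28 window in Table 2 with the schedule, which gives none, so that deaths after Day 28 are not counted in category 1.

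The cost is some SAP wording and one extra block of rows from data already to be collected. The table becomes slightly longer, and the stayers' intervals will be wide, particularly within severity groups.
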